#### **Exclusion criteria**

- Patient/ family members who do not give consent to participate in the study.
- Patients with age less than 18 years
- Patients presenting with multi-organ failure
- Pregnancy
- Individuals with HIV and Viral Hepatitis and Cancer
- Extremely moribund patients with an expected life expectancy of less than 24 hours
- Hemodynamic instability requiring vasopressors
- Previous history of allergy to plasma
- Cirrhosis
- Severe renal impairment with GFR < 30ml/min or recipients of RRT, peritoneal dialysis
- Patients with uncontrolled diabetes mellitus, hypertension, arrhythmias and unstable Angina

#### **Transfusion of COVID-19 Convalescent Plasma**

Dose-250 ml

Frequency – 2 doses on consecutive days

Duration –Start by day 3 of symptom onset in eligible patients

#### **Blood Group Compatibility**

ABO identical plasma will be the first choice followed by ABO compatible plasma.

In case compatible plasma is not available reduction of titers will be done using an ABO antibody immune-adsorption column.

[figure not shown]
#### **Patient Monitoring**

All included patients will be randomized to receive either 500 ml of convalescent plasma in two doses of 250 ml on two consecutive days along with the standard of care or standard of care alone

Clinical information of all enrolled patients including symptoms at presentation, time to presentation to the hospital, and development of pulmonary symptoms will be recorded. The details of comorbid diseases as measured by the Charlson index of co-morbidity and Acute Physiology and Chronic Health Evaluation II (APACHE II). Details of cross-sectional imaging, chest-x-ray, bacterial or fungal co-infections, and details of antibiotic treatment will be recorded. Development of complications including shock, acute kidney injury, acute coronary syndrome, myocarditis, acute respiratory distress syndrome, need for mechanical ventilation and nosocomial infection will be recorded. The use of high-flow oxygen, non-invasive, and invasive ventilation will follow standard guidelines and will be recorded. The details of antiviral treatment will be recorded for all enrolled patients.

[name] [name], MD  
Additional Professor - Transfusion Medicine  
Institute of Liver and Biliary Sciences  
[name]  
[name]

## Flow Chart

- All variables shall be expressed in mean (SD) or median (range)
- Variables will be compared by Mann- Whitney U test
- For Categorical variables, we will use Chi-Square or Fisher's test
- Survival analysis will be done using Cox-proportional regression analysis

The actuarial probability of survival shall be calculated by Kaplan- Meier graph and compared by the log-rank test.

[name] [name], MD  
Additional Professor - Transfusion Medicine  
Institute of Liver and Biliary Sciences  
[name]  
[name]

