### Section 13: Study Design

#### Aim and Objectives

**Primary Objective:** To study the efficacy of convalescent plasma in severe COVID 19 patients in time to clinical improvement (Clinical improvement: Reduction of two points in ordinal scale or live discharge from the intensive care unit, whichever is earlier)

The six-point scale is as follows:

1. *death=6;*
2. *hospital admission for extracorporeal membrane oxygenation or mechanical ventilation=5;*
3. *hospital admission for non-invasive ventilation or high-flow oxygen therapy=4;*
4. *hospital admission for oxygen therapy (but not requiring high-flow or non-invasive ventilation)=3;*
5. *hospital admission but not requiring oxygen therapy=2;*
6. *discharged or having reached discharge criteria (defined as clinical recovery—ie, normalization of pyrexia, respiratory rate 94% on room air, and relief of cough, all maintained for at least 72 h)=1.*

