#### Secondary Objectives:

1. The proportion of patients in each category according to the ordinal scale at 48 hours and day 7, 14, and 28 after randomization
2. Duration of oxygen therapy
3. Duration of hospital stay
4. The proportion of patients on mechanical ventilation at day 7.(after randomization)

[name] [name], MD  
Additional Professor - Transfusion Medicine  
Institute of Liver and Biliary Sciences  
[name]  
[name]

5. Mortality at day 7 and day 28 (after randomization)
6. Duration of Intensive Care Unit stay
7. Incidence of adverse effects in both groups
8. Presence of antibodies against SARS-CoV-2 in serum on days 0, 3, 7, 14, 21 & 28 after plasma administration, as long as the patient remains in the hospital.
9. Cytokines and acute phase reactants
10. To study the titers in COVID-19 convalescent plasma donors and correlate with duration of illness, the severity of symptoms, duration of hospital stay, drugs used in therapy, duration between recovery, and donation.

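### The plain Mann-Whitney test on oxygen, hospital and ICU durations has no rule for deaths, so an early death scores as a short and therefore good duration

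*Protocol*

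**What the plan says.** The statistical methods are a short list of bullets under the Flow Chart heading.

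- For variables that are not categorical: "Variables will be compared by Mann- Whitney U test".
- For the rest: "For Categorical variables, we will use Chi-Square or Fisher's test".
- For time-to-event data: "Survival analysis will be done using Cox-proportional regression analysis", and "The actuarial probability of survival shall be calculated by Kaplan- Meier graph and compared by the log-rank test".

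The first rule takes in Secondary Objectives 2 ("Duration of oxygen therapy"), 3 (hospital stay) and 6 (ICU stay). The second takes in Secondary Objective 4, "The proportion of patients on mechanical ventilation at day 7". None of these has a rule for patients who die.

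Elsewhere the protocol does treat death as unfavourable. In Aim and Objectives death scores 6, the worst category, and clinical improvement is defined as "Reduction of two points in ordinal scale or live discharge from the intensive care unit, whichever is earlier". Secondary Objective 1 reports "The proportion of patients in each category according to the ordinal scale at 48 hours and day 7, 14, and 28 after randomization", and Secondary Objective 5 is mortality at days 7 and 28.

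**The concern.** Oxygen therapy, ICU stay and hospital stay all end when the patient dies. If the observed length goes into a rank test in which shorter is better, death on day 2 looks like recovery on day 2. An arm with more early deaths can then show shorter stays, even though survivors fare the same in both arms. The test would be pointing in the opposite direction to the protocol's own ordering of outcomes.

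Deaths are unlikely to be rare. Table 2 of the protocol quotes 14.9% seven-day mortality from a report on 5,000 transfused patients. Eligibility here requires two severity criteria, one of which is ventilation.

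Ventilation at day 7 raises a related problem. A patient dead by day 7 is not on a ventilator, so counts as a success if kept in the denominator. If dropped, the comparison is restricted by an event after randomisation. The protocol does not say which applies.

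**Working it through.** **What can be reproduced.** The protocol gives no power, alpha, effect size or event rate. Only the allocation can be checked: 150/50 = 3, which agrees with 3:1.

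**Inputs.** From the protocol: 150 v 50. Assumed: two-sided 0.05; survivors' duration lognormal with median 12 days and log-SD 0.5 in both arms, capped at 28; decedents' duration lognormal with the same log-SD and median 4, 6 or 12 days; mortality 20% on control and 30% or 40% on plasma. Because survivors' stays are the same in both arms, any significant result for plasma is false.

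**By hand.** Let p_T and p_C be mortality on plasma and control, and θ the chance that a decedent's duration is shorter than a survivor's. The Mann-Whitney test compares with 0.5 the chance that a plasma patient has the shorter duration:

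index = 0.5 + (p_T − p_C)(θ − 0.5)

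- Median 4 days: θ = Φ(ln(12/4)/(0.5√2)) = 0.940, so at 40% v 20% the index is 0.5 + 0.2 × 0.440 = 0.588.
- Median 6 days: θ = Φ(ln(12/6)/(0.5√2)) = 0.837, index 0.567.
- Median 12 days: θ = 0.5, index 0.5. The test is neutral.
- Death ranked worst: θ is replaced by 0, so the index is 0.5 − 0.2 × 0.5 = 0.40, correctly favouring control.

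The null standard error is √(201/(12 × 150 × 50)) = 0.0473. For median 4 days, z = 0.088/0.0473 = 1.86, and the chance of exceeding 1.96 is about 46%. For median 6 days, z = 1.42 and the chance is about 30%.

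**Simulation (1,500 trials per row).** Share of trials with a significant result:

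| Mortality, plasma v control | Decedents' median | Raw duration: favours plasma | Death worst: favours control |
|---|---|---|---|
| 20% v 20% | 4 days | 2.5% | 2.4% |
| 30% v 20% | 4 days | 12.5% | 17.8% |
| 30% v 20% | 6 days | 11.5% | 17.9% |
| 30% v 20% | 12 days | 2.0% | 17.1% |
| 40% v 20% | 4 days | 45.3% | 60.9% |
| 40% v 20% | 6 days | 28.7% | 58.3% |
| 40% v 20% | 12 days | 1.8% | 57.4% |

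The 45.3% and 28.7% agree with the hand figures. Where plasma mortality is higher, ranking death worst favours plasma in at most 0.1% of trials.

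**Time to clinical improvement, only if deaths were censored when they occur.** Assume an improvement hazard of −ln(0.25)/28 = 0.0495 per day in both arms, and death hazards of 0.040 (plasma) and 0.015 (control).

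- One minus Kaplan-Meier at day 28 is 1 − exp(−0.0495 × 28) = 75% in both arms.
- Cumulative incidence is h/(h+d) × [1 − exp(−28(h+d))], where h is the improvement hazard and d the death hazard. It gives 51% on plasma and 64% on control, with 41% and 19% dead.
- The log-rank test shows harm in 3% of 3,000 simulated trials with deaths censored, and in 30% with deaths kept at risk to day 28.

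**The case against.** **The protocol does count death as bad.** It does so in the ordinal scale, in mortality at days 7 and 28, and in the survival analysis. This stands. It would be too broad to say that the stated tests in general treat death as neutral or favourable. The point is confined to the three durations and, subject to its denominator, ventilation at day 7. Separate mortality results would put a misleading duration result in context, but would not correct it.

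**Death rules belong in the SAP.** In part. A missing rule alone would not be a finding. Here, though, the protocol fixes an unqualified test, and a SAP that ranked death worst would be adding to it. The trial is open-label, so that choice is better made early.

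**The magnitude is assumed.** This stands. No mortality rate or length of stay in the simulation comes from the protocol, and the largest figures need mortality to double on plasma and deaths to come early. The seven-day mortality in Table 2 makes early death plausible, but comes from a different population.

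**The primary analysis.** A reader might infer that Kaplan-Meier and Cox would censor deaths in the primary endpoint. The documents do not say so. Kaplan-Meier and log-rank are attached to the probability of survival, where death is the event, and Cox to survival analysis. No sentence assigns them to time to clinical improvement or gives a censoring rule. Even if they were used that way, the result would be masking (75% v 75%), not reversal. A cause-specific hazard ratio is also a legitimate estimand.

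**Ventilation at day 7.** Counting the dead as not ventilated depends on an unstated denominator. Categories 5 and 6 of the ordinal scale at day 7 already let the reader add ventilated and dead together.

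**Conclusion.** The concern holds for the durations of oxygen therapy, hospital stay and ICU stay. The stated Mann-Whitney test, applied to observed lengths, rewards early death and contradicts the protocol's placing of death as the worst outcome. At an assumed mortality of 40% v 20%, it falsely favours plasma in about 29% to 45% of trials when decedents' median duration is 4 to 6 days against 12 in survivors, and in about 2% when the medians are equal. At 30% v 20% with early deaths it does so in about 11% to 12%. The direction of the bias therefore depends on deaths being early, and its size also on the mortality difference.

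These are secondary outcomes, so a wrong direction for the primary conclusion does not follow. For time to clinical improvement, what the text supports is narrower: no method is explicitly named, and how death enters is left open.

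**What to change.** - **Durations.** Keep the Mann-Whitney test but give every patient who dies the worst rank. Alternatively, analyse days alive and free of oxygen, ICU and hospital to day 28, with death scored 0. Report raw durations in survivors descriptively.
- **Day 7.** Report on mechanical ventilation or dead, with all randomised patients in the denominator.
- **Time to clinical improvement.** Name the method. If the listed Kaplan-Meier, log-rank and Cox tools are used, keep deaths as not improved to the end of follow-up (for example day 28) and show cumulative incidence, instead of censoring at the time of death.

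The wording takes a few lines, but the change is not free of cost. Monitoring is planned daily until clinical improvement (under Details of Standard of Care), so oxygen, ICU and hospital status after improvement or discharge, including readmission, must be known to day 28. The day-28 ordinal and mortality assessments are already planned and could be used to collect it. The new measures also read less directly as length of stay, which is why survivors' raw durations should remain as description.

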**Table 2: Serious Adverse Event (SAE) associated with convalescent plasma transfusion (n=5,000)**

Four hour mortality reports	Reported(n=36)	Related(n=25)	Estimated(95% CI)
Mortality	15	4	0.08% (0.03%, 0.21%)
Transfusion associated circulatory overload(TACO)	7	7	0.14% (0.07%, 0.29%)
Transfusion related acute lung injury(TRALI)	11	11	0.22% (0.12%, 0.39%)
Severe allergic transfusion reaction	3	3	0.06% (0.02%, 0.18%)
Seven Day reports	Reported		Estimated(95% CI)
Mortality	602		14.9% (13.8%, 16.0%)

**Donor Safety:** The convalescent plasma donation by Plasmapheresis was found to be a safe procedure in the RCT done at ILBS-MAMC. No adverse events were noted during 16 procedures done under this trial. No other studies reported any SAEs during donor plasmapheresis

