**Study Design:**

An open label randomized controlled trial.

The study group will comprise of adult patients with severe COVID -19 as detailed above. Randomization will be done in the ratio of 3:1 in with 150 patients in the treatment arm and 50 patients in the control arm. Allocation concealment will be done by Sequentially Numbered Opaque Sealed Envelopes (SNOSE) method.

[name] [name], MD  
Additional Professor - Transfusion Medicine  
Institute of Liver and Biliary Sciences  
[name]  
[name]

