### Justification for Unequal Allocation

We want to collect the additional safety profile associated with convalescent plasma group hence enrolling more number of cases in this group.

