### Details of Standard of Care

The Ministry of Health and Family Welfare has issued detailed guidelines for the management of sCOVID-19 based on varying grades of severity which may be periodically updated. For the management of ARDS or sepsis the respective guidelines issued by ARDSNet and Surviving Sepsis campaign will be followed. Other institutional protocols for supportive management will be implemented. (ref: Guidelines on Clinical Management of COVID-19. MoHFW, GoI.2020.)

**Monitoring and Assessment:** Daily until clinical improvement

**Adverse Effects:** Will be documented

**Stopping rule:** None

**(C) The expected outcome of the project:** We expect convalescent plasma therapy to be a safe and efficacious therapy based on our pilot RCT. This study will determine if there is clinical improvement /mortality benefits and further elaborate on its safety in patients with severe COVID-19

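### The 3:1 allocation was chosen to learn about plasma safety, but the only stated method that covers adverse effects is a between-arm test with little power at 150:50; interval estimation would serve that purpose better at almost no cost.

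*Protocol*

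**What the plan says.** Under Study Design: "Randomization will be done in the ratio of 3:1 in with 150 patients in the treatment arm and 50 patients in the control arm". The Justification for Unequal Allocation gives one reason: "We want to collect the additional safety profile associated with convalescent plasma group hence enrolling more number of cases in this group".

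Item 7 of the Secondary Objectives is "Incidence of adverse effects in both groups". In Section 13, after the details of standard of care, the entry for adverse effects reads "Will be documented". The expected-outcome paragraph in the same section says "We expect convalescent plasma therapy to be a safe and efficacious therapy based on our pilot RCT" and adds that the study will "further elaborate on its safety in patients with severe COVID-19".

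The statistical methods are a short list printed under the heading Flow Chart. The line that covers proportions is "For Categorical variables, we will use Chi-Square or Fisher's test". It does not mention adverse effects. The list names no confidence interval, risk difference or upper bound for any outcome, and no significance level.

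Table 2 gives background rates from 5,000 plasma-treated patients: TRALI 11, TACO 7 and severe allergic reaction 3.

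**The concern.** The allocation and the stated method pull in different directions. Moving patients from control to plasma makes the plasma-arm event rate more precise. It makes a test between the arms weaker, because the comparison is limited by the 50 controls. The reason given for 3:1 is a reason for estimating a rate, while the only method on the page that reaches adverse effects is a significance test.

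The test is also poorly matched to the harms in Table 2. A patient given no plasma cannot have a reaction to it, so the control count for such events is zero by construction and a p-value against it carries little information.

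What is at stake is how much the trial can say about safety. The 150 plasma patients support a rate and an upper limit. A bare p-value uses little of that and would often be non-significant even if harm were real.

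**Working it through.** **Inputs.** 150 and 50 patients (Study Design); TRALI 11, TACO 7 and severe allergic reaction 3 in 5,000 (Table 2). The protocol states no alpha, so two-sided 0.05 is assumed. It gives no control-arm adverse-event rates either, so a range is assumed. There is no planned safety figure to reproduce; only the split can be checked: 150/50 = 3.

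**1. Smallest zero-control excess that Fisher's test detects.** With 11 events in all, the number falling in the plasma arm is hypergeometric: P(k) = C(150,k)·C(50,11−k)/C(200,11). The observed table has P(11) = 0.0384. Tables no more probable are k ≤ 5, with P(5) = 0.0242, P(4) = 0.0052, P(3) = 0.0008 and P(2) = 0.0001. The two-sided p is 0.0384 + 0.0303 = 0.0687.

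| Plasma vs control | Fisher, two-sided | Chi-square, uncorrected | Chi-square, Yates |
|---|---|---|---|
| 10/150 vs 0/50 | 0.069 | 0.061 | 0.134 |
| 11/150 vs 0/50 | 0.069 | 0.049 | 0.107 |
| 12/150 vs 0/50 | 0.040 | 0.039 | 0.086 |
| 15/150 vs 0/50 | 0.025 | 0.020 | 0.044 |

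The uncorrected chi-square for 11 vs 0 is 200·(11·50)²/(150·50·11·189) = 3.88. One-sided Fisher for the same table gives 0.038. The smallest expected count is 11·50/200 = 2.75, below 5, so Fisher would be the usual choice. With 100 per arm, 6 vs 0 already gives p = 0.029.

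**2. Power.** This is the sum of binomial probabilities over all tables with a higher plasma rate and two-sided Fisher p < 0.05. All rates are assumed.

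| Control vs plasma rate | Power at 150:50 | Power at 100:100 |
|---|---|---|
| 0% vs 3% | 0.002 | 0.081 |
| 0% vs 5% | 0.074 | 0.384 |
| 5% vs 10% | 0.143 | 0.190 |
| 10% vs 20% | 0.322 | 0.444 |
| 20% vs 30% | 0.256 | 0.313 |

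Power is lower at 3:1 in every row, but it is also low at 1:1.

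**3. What the plasma arm alone can say.** The Table 2 reactions sum to 21/5,000 = 0.42%. In 150 patients that is 150 × 0.0042 = 0.63 expected events, or 300 × 0.0042 = 1.26 if the rate is applied to each of two transfusions. Exact (Clopper-Pearson) 95% limits are:
- 0/150: upper limit 1 − 0.025^(1/150) = 2.4%.
- 11/150 = 7.3%: 3.7% to 12.7%.

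The lower limit of 3.7% is nearly nine times 0.42%. The 11 events that Fisher's test leaves at p = 0.069 would stand out plainly against the protocol's own background figures.

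**4. The same 11 events as a risk difference.** Wilson limits are 4.14% to 12.65% for 11/150 and 0% to 7.13% for 0/50. Newcombe's interval has lower limit 7.33 − √[(7.33 − 4.14)² + 7.13²] = −0.5% and upper limit 7.33 + (12.65 − 7.33) = 12.7%. The interval adds no power, but it shows that an excess of up to 12.7 percentage points has not been excluded.

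**The case against.** The strongest objection is that the protocol does not tie safety to this test. The chi-square/Fisher line is generic, while the safety passages speak of incidence, documentation and a safety profile, all of which are descriptive. A reader might infer that safety is to be decided by p > 0.05 and that 11 serious reactions against none would be declared safe. The documents do not support that: no passage sets a safety hypothesis, a significance level or a rule that non-significance means safe. The statement that plasma is expected to be safe is an expectation from the pilot, not a criterion. This part of the objection stands in full.

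The 11-event illustration also depends on the test. The protocol allows either test, and uncorrected chi-square gives p = 0.049 for the same table. Transfusion reactions would naturally be listed for the plasma arm anyway, and eleven of them would be noticed whatever the p-value. That stands too, so the example shows weak power and does not predict what would be reported.

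Low power for harms is largely a limit of 200 patients; equal allocation would not cure it. The protocol sets no power target for a secondary safety outcome, so none is missed.

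Finally, intervals and safety reporting rules are often left to a statistical analysis plan, which is not at hand, and naming a test does not forbid reporting intervals. This keeps the point from being an error. It does not remove the mismatch on the page: the allocation was chosen to describe plasma safety, and the one method stated that reaches adverse effects compares arms.

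**Conclusion.** The point holds as an improvement, not as an error in the plan as written. The only stated method that covers adverse effects in both groups is a between-arm significance test. The 3:1 split weakens it, and it says little about reactions that only plasma recipients can have.

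In size: with no control events, two-sided Fisher needs 12/150 (8.0%) to reach p < 0.05, and power runs from 0.002 to 0.32 over the contrasts examined. The plasma arm alone, with no events, would exclude rates above about 2.4%. That is more informative than a p-value, though still well above the 0.42% in Table 2.

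These figures assume a two-sided alpha of 0.05, the listed event rates and complete data on all 200 patients. The 12-event threshold is specific to Fisher's test; the low power across the other contrasts does not rest on that one table.

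**What to change.** In the statistical methods listed under Flow Chart, add for adverse effects:

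- For events possible in both arms, report the plasma-minus-control risk difference with a 95% confidence interval (for example Newcombe's).
- For transfusion-specific reactions, report the plasma-arm rate with its exact 95% interval, set beside the Table 2 rates.
- State that a non-significant difference will not be taken as evidence of safety.

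In the Justification for Unequal Allocation or the expected-outcome paragraph, state what the plasma arm can show: with no events, 150 patients exclude only rates above about 2.4%.

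The cost is a few sentences. Allocation, sample size, visits and data collection stay unchanged. The downside is a more modest safety statement, limited to the rates that the trial can exclude.

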### Sample Size calculation:

The study will be designed as an open label RCT with an aim to enrol 150 patients in the treatment arm and 50 patients in the control arm.

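### On its natural reading, the plan compares the ordered six-point scale in secondary objective 1 with an unordered test; it should name an ordinal method

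*Protocol*

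**What the plan says.** Under Aim and Objectives the protocol introduces an ordered scale ("The six-point scale is as follows"), scored from 6 for death down to 1 for discharge or readiness for discharge. The scale is used twice:

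- In the primary objective, as part of a time-to-event definition: "Reduction of two points in ordinal scale or live discharge from the intensive care unit, whichever is earlier".
- In secondary objective 1, as a distribution at four fixed times: "The proportion of patients in each category according to the ordinal scale at 48 hours and day 7, 14, and 28 after randomization".

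The statistical methods are short generic lines under the heading Flow Chart. Two could bear on secondary objective 1:

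- "Variables will be compared by Mann- Whitney U test", which does not say which variables are meant.
- "For Categorical variables, we will use Chi-Square or" Fisher's test, again without naming any endpoint.

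The other lines deal with descriptive summaries and survival methods. No trend test or proportional-odds model is named, and no line is tied to the ordinal scale. Study Design fixes the allocation: "Randomization will be done in the ratio of 3:1 in with 150 patients in the treatment arm and 50 patients in the control arm".

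**The concern.** The methods separate categorical variables from the rest, and secondary objective 1 is worded as proportions per category. Read together, they send the ordinal outcome to chi-square or Fisher.

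Both tests treat the six states as unordered labels. On a 2×6 table the Pearson test has (2 − 1) × (6 − 1) = 5 degrees of freedom, and its p-value is the same however the columns are permuted: exchanging the death and discharge columns changes nothing. A significant result would not say which arm did better and would bring no single effect estimate. A consistent moderate shift towards better states, which is what an effective treatment would be expected to produce, could be missed because the test spreads its power over every possible pattern of difference.

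**Working it through.** **Inputs from the protocol.** Six levels and four time points (Aim and Objectives, Secondary Objectives). Arm sizes 150 and 50 (Study Design; Sample Size calculation: "with an aim to enrol 150 patients in the treatment arm and 50 patients in the control arm"). The protocol gives no power figure for this outcome, and the total of 200 cannot be reproduced because no alpha, power, effect size or control rate is stated.

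**Assumptions.** Two-sided 5%, no dropout, a proportional shift with common odds ratio (OR) 1.5 to 3.0, and five illustrative control distributions (percent at scores 1 to 6):

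- flat: one sixth each
- 48 h-like: 1/4/40/35/15/5
- day 7-like: 10/15/30/20/15/10
- day 14-like: 35/15/15/10/10/15
- day 28-like: 55/8/7/5/5/20

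**Formulas.** The treatment distribution multiplies each cumulative odds of being at or below a score by the OR. The unordered test is Pearson's chi-square, with empty columns dropped. The ordered test is Mann-Whitney with tie-corrected variance n₀n₁/12 × [(N + 1) − Σ(t³ − t)/(N(N − 1))], where t is the total in each category.

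**One case by hand (flat control, OR 2.0).**

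1. The control cumulative odds 0.2, 0.5, 1, 2, 5 become 0.4, 1, 2, 4, 10. The treatment proportions are then 0.286, 0.214, 0.167, 0.133, 0.109, 0.091.
2. The pooled proportions, 0.25 × control + 0.75 × treatment, are 0.256, 0.202, 0.167, 0.142, 0.123, 0.110.
3. Σ(difference)²/pooled = 0.0554 + 0.0112 + 0 + 0.0078 + 0.0268 + 0.0522 = 0.1535 (from unrounded terms).
4. The noncentrality is (50 × 150/200) × 0.1535 = 37.5 × 0.1535 = 5.76.
5. With 5 df (critical value 11.07), power is 41.6%. If one degree of freedom carried the same noncentrality (critical value 3.84), power would be 67.0%.
6. Simulation of this case gives 42.7% for chi-square and 66.5% for Mann-Whitney, in agreement.

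**All cases, 20,000 simulated trials each; ranges are over the five distributions.**

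| Common OR | Chi-square | Mann-Whitney | Gap (points) |
|---|---|---|---|
| 1.0 (null) | 4.5–4.9% | 4.8–5.2% | – |
| 1.5 | 14–18% | 26–29% | 9–13 |
| 1.75 | 24–30% | 42–49% | 14–21 |
| 2.0 | 37–44% | 57–67% | 18–26 |
| 2.25 | 50–58% | 70–80% | 19–26 |
| 2.5 | 61–69% | 79–88% | 18–23 |
| 3.0 | 76–86% | 90–96% | 11–15 |

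Another assumed day-14 control distribution (35/12/18/10/7/18, 3,000 runs) gives 44% versus 65% at OR 2.0 and 68% versus 87% at OR 2.5, gaps of 21 and 19 points.

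**Check independent of any distribution.** The noncentrality that gives a 1-df test 80% power is (1.960 + 0.842)² = 7.85. A 5-df test with the same noncentrality has 55.5%.

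**The case against.** The strongest objection is that the protocol never assigns the scale to chi-square or Fisher. A reader might infer that it prescribes an unordered test for this outcome, but the documents do not go that far. The Mann-Whitney line names no variables, the scale carries numerical scores, and a rank test respects their order. This stands: the chi-square reading is the natural one, but it is an inference. A statistical analysis plan, not available here, may settle it. What remains is that two different tests are open for one endpoint, and the wording of the objective favours the weaker.

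A reader might also quote a flat 20-point loss. The protocol supplies none of the inputs for such a figure. It depends on the assumed odds ratio and control distribution, and it presumes a proportional shift, the pattern that suits a rank test best.

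Nor is an unordered result without value. If plasma moved patients into both the best and the worst states, that would be an important benefit-harm signal, given the transfusion-related lung injury, circulatory overload and deaths listed in the protocol's Risks section. A common odds ratio could average such a split away, while an unordered test keeps power against it.

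Finally, one might count 6 × 4 = 24 separate category tests. The protocol does not propose category-by-category testing, so that multiplicity charge is not supported.

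**Conclusion.** The point holds as a gap in the methods on a secondary outcome. The natural reading sends an ordered endpoint to a test that ignores order, the alternative reading is not excluded, and the protocol should say which applies.

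If the categorical rule is followed, the loss against a rank test is roughly 10 to 25 points of power, and about 20 at odds ratios of 2.0 to 2.5. This rests on 150 versus 50 patients, two-sided 5%, no dropout, a proportional shift and the assumed control distributions. Under a non-monotone effect the unordered test need not be weaker.

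A reader might infer that the planned test is invalid or that the main result is compromised. Neither follows. Chi-square holds its 5% error rate in these simulations, and the primary outcome, time to clinical improvement, does not depend on this comparison.

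**What to change.** Add one sentence to the statistical methods: the ordinal score (death = 6) at 48 hours and days 7, 14 and 28 is compared between arms by an ordinal method. This can be either the Mann-Whitney test already listed or a proportional-odds model adjusted for baseline score, reported as a common odds ratio with 95% confidence interval. Keep the category percentages alongside, as the objective asks, so that any benefit-harm split stays visible.

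The cost is small. The software is standard. The scores at the four times are what objective 1 itself requires, and a baseline score is needed anyway for the two-point criterion in the primary objective. Because Monitoring and Assessment describes daily follow-up only up to clinical improvement, it is worth confirming that scores on the later fixed days are also recorded for patients who have already improved. The one statistical downside is that a common odds ratio assumes proportional odds. That should be checked, and the percentages relied on where it fails.
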